- ***Digit-Symbol Substitution Test from the Wechsler Adult Intelligence Scale-Revised (WAIS-R).*** The Digit Symbol Substitution test (Wechsler 1981) is a subset from the WAIS-R. The test consists of small blank squares presented in rows with one of 9 numbers (1-9) randomly printed directly above each blank square. A “key” is printed above the rows of blank squares. The “key” pairs numbers 1 through 9 with an unfamiliar symbol. Following a short series of practice trials, the subject must use the key to fill in the blank squares in order (working from left to right across the rows) with the symbol that is paired with the number over the blank square. The subject must work as fast as possible for 90 seconds. The measure of interest is number of squares filled in correctly within the time limit (maximum raw score = 91). This test engages multiple cognitive abilities including attention, psychomotor speed, complex scanning, visual tracking, and immediate memory.
- ***MMSE Total Score.*** The MMSE (Folstein et al. 1975) is a brief, frequently used screening instrument for Alzheimer’s disease drug studies. The MMSE scale evaluates orientation, memory, attention, concentration, naming, repetition, comprehension, and ability to create a sentence and to copy 2 overlapping pentagons. The MMSE is scored as the number of correctly completed items with a lower score indicative of poorer performance and greater cognitive impairment. The total score ranges from 0 (worse) to 30 (perfect performance).

Each component score is divided by the baseline SD of that component, to form standardized Z-scores. These Z-scores are summed to form the composite, so that a 4-point change on the composite is approximately equivalent to a change of 1 baseline SD on each component.

The administration of the PACC should be recorded (audio only) for quality review purposes according to locally applicable laws and regulations.

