10.1.2.2. Clinical Dementia Rating Scale

The CDR (Morris 1993) is a clinical scale that rates the severity of dementia as absent, questionable, mild, moderate, or severe (CDR score of 0, 0.5, 1, 2, or 3, respectively). The score is based on interviews with the subject and study partner, using a structured interview that

assesses 6 domains: memory, orientation, judgment and problem solving, community affairs, home and hobbies, and personal care. The ratings of degree of impairment obtained on each of the 6 categories of function are synthesized into 1 global rating of dementia (ranging from 0 to 3), with more refined measure of change available by use of the Sum of Boxes (CDR-SB). Reliability and validity has been established, as has high inter-rater reliability.

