5.1. Primary Objective

The primary objective of this study is to test the hypothesis that solanezumab, administered as an IV infusion every 4 weeks for 4.5 years, will slow cognitive decline as compared with placebo in participants with preclinical AD. The primary objective will be assessed using a constrained Longitudinal Data Analysis (cLDA) Natural Cubic Spline (NCS) analysis (referred to as NCS henceforth) of the primary outcome measure, the Preclinical Alzheimer Cognitive Composite (PACC), a composite that is primarily weighted on episodic memory and executive function tests, in which the specific hypothesis is that the cognitive decline at 240 weeks will be significantly less for solanezumab than for placebo.

The PACC will be composed of 4 components: the total score from the free and cued selective reminding test (FCSRT), the delayed paragraph recall on the logical memory IIa test from the Wechsler Memory Scale, the digit-symbol substitution test from the Wechsler adult intelligence scale-revised, and the MMSE total score. Specifically, for the FCSRT, the total will be the sum of the free and cue score plus the free recall score, resulting in a total from 0 to 96. Each component score is converted to a z-score by subtracting the baseline mean for that component and dividing by the baseline standard deviation for that component. The PACC is the sum of the four resulting z-scores.

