6.2. Determination of Sample Size

In order to develop an appropriate measure of cognitive decline in a preclinical population, we tested several combinations of measures using data from longitudinal studies in clinically normal populations, including the ADNI; the AIBL; the ADCS-PI trial; and the HABS.

Sample size and power at 4.5 years (240 weeks) for the PACC were estimated using data from ADNI and HABS. Estimates were obtained by applying appropriate assumptions regarding treatment difference, SD, and attrition for a 4.5-year study in a preclinical AD population. In ADNI, the difference in the composite change between participants with and without elevated brain amyloid at 240 weeks was 2.13 (SD=2.85). Similarly, in HABS, the difference in the composite change between participants with and without elevated brain amyloid at 240 weeks was 2.66 (SD=3.08). Given the ADNI-derived estimate of SD at 240 weeks of SD=2.85 and 30% attrition, the total N=1150 provides 80% power (5% 2-sided alpha) to detect a treatment difference of 0.532 points or $0.532/2.13 = 24.9\%$ of the amyloid group difference. Similarly, based on the HABS estimate of SD at 240 weeks of SD=3.08, the study has 80% power to detect a treatment difference of 0.570 points or $0.570/2.66 = 21.4\%$ of the amyloid group difference.

For the open-label period, the estimated mean PACC difference between cognitively normal participants with and without elevated brain amyloid at 336 weeks is 2.95 (SD=3.77) based on ADNI and 4.74 (SD=3.99) based on HABS. Accounting for the administrative censoring that will be induced by the common close design of the open-label period, and assuming an overall attrition rate of 30%, about 266 PACCs are expected to be available at 336 weeks. The visit-to-visit correlation is estimated to be about 0.5. Under these pilot estimates, 266 PACCs at 336 weeks would provide 80% power to detect a randomized group (early-start vs delayed-start treatment with solanezumab) difference of about 0.9 PACC points. This change of 0.9 PACC points reflects 30% of the difference between amyloid-positive and -negative participants based on ADNI, and 20% of that difference based on HABS.

Sample size for the study was determined assuming an MMRM analysis prior to the interruption caused by the COVID-19 pandemic. Applying the NCS approach in simulated trials with a COVID-19 pandemic interruption suggests the study has 94% power to detect an effect size of 0.75 PACC points at 240 weeks.

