7.2. Handling of Dropouts or Missing Data

If any of the individual items for any of the clinical scales are missing or unknown, every effort will be made to obtain the score for the missing item or items. For the primary outcome (PACC), if one of the four components is missing, the total score will be imputed. The sum of the other three components will be prorated to the sum of total components. The imputed number will be rounded up to the nearest integer. If the nearest integer is greater than the maximum possible score, the imputed score will be equal to the maximum score. If more than one of the components is missing, the PACC at that visit will be considered missing.

For the ADL Prevention Questionnaire, if $\leq 30\%$ of the items are missing, the total score will be imputed. The sum of the non-missing items will be prorated to the sum of total items. The imputed number will be rounded up to the nearest integer. If the nearest integer is greater than the maximum possible score, the imputed score will be equal to the maximum score. If $>30\%$ of the items are missing, the total score at that visit will be considered missing.

The same imputation technique will be applied to the CFI, CDR-SB and MMSE.

For the FCSRT, the total score will be imputed if only 1 of the three trials of cued scores is missing – if any of the free recall scores are missing or if more than 1 cued recall scores are missing, the total will not be imputed and will be considered missing. The imputation will rely on the sensitivity to cueing measure, which is defined as the number of correct cued responses divided by the total number of cued responses across the two completed trials. For instance, if a participant was cued on 10 items and correctly answered on 8 of them, the sensitivity to cueing measure would be 0.8. This value will then be multiplied by the number of items the participant should have been cued on for the missing trial and the resulting value will be rounded to the nearest integer.

For all other scales, if any item is missing, any total or sum involving that item will be considered missing.

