7.9. Efficacy Analyses

7.9.1. Analysis of Primary Outcome (Placebo-Controlled Period)

7.9.1.1. NCS Analysis of Primary Outcome

The primary objective of this study is to test the hypothesis that intravenous infusion of solanezumab will slow cognitive decline in preclinical AD as compared with placebo.

The original mITT analysis (that is, all participants as randomized to treatment who have a baseline and at least 1 postbaseline measure) for the primary outcome will be retained and conducted at the end of the treatment period, although the dose was increased during the study and dosing and assessments were interrupted due to COVID-19; in other words, the primary analysis will include all data for the solanezumab group as the treatment group versus placebo. As with the original analysis plan, the hypothesis for this analysis will be tested against a two-sided alpha level of .05.

The details of this analysis including the analytic method and model are presented below.

An NCS analysis with 2 degrees of freedom will be used to assess the difference between treatment groups in change from baseline for the PACC score at 240 weeks. The composite score at baseline and each post-baseline visit will be the dependent variable. Time will be treated as a continuous variable with values equal to the years between baseline and follow-up exam dates. We will assume an unstructured covariance structure, where the time values are mapped back to the corresponding visits. The NCS basis expansion will assume an interior knot at the median of observation times, and boundary knots at zero years and the maximum follow-up (Hastie 1992). The fixed effects will include the following terms: (i) NCS basis expansion terms (two terms), (ii) NCS basis expansion terms-by-treatment interaction (two terms), (iii) PACC test version administered, (iv) age, (v) education, (vi) APOE4 Carrier Status (yes/no), and (vii) baseline florbetapir cortical SUVr. The model is constrained to not allow a difference between treatment group means at baseline.

The null hypothesis is that the treatment difference between solanezumab and placebo for the PACC score at 240 weeks is equal to zero. The primary analysis will be carried out in the mITT population that is randomized and has a baseline score and at least 1 post-baseline assessment. If the unstructured covariance structure matrix results in a lack of convergence, the following structures will be used in sequence:

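### SAP 7.2 rounds an imputed PACC up to a whole number although the PACC is a sum of z-scores; the effect on the treatment contrast is small, but the scoring rule is wrong as written

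*SAP*

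**What the plan says.** SAP 5.1 standardises each component by subtracting its baseline mean and dividing by its baseline SD, and then states: "The PACC is the sum of the four resulting z-scores". The result is non-integer, can be negative and is centred near zero at baseline.

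SAP 7.2 covers a visit at which exactly one of the four components is missing. The sum of the other three is "prorated to the sum of total components. The imputed number will be rounded up to the nearest integer". If that integer exceeds the highest possible score, the highest score is used instead. No highest score is given for the PACC. The next paragraph of SAP 7.2 uses the same wording for the ADL Prevention Questionnaire, which is an item sum, and then adds: "The same imputation technique will be applied to the CFI, CDR-SB and MMSE".

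For a partly missing FCSRT, the same section says "the resulting value will be rounded to the nearest integer", without the word up.

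Protocol 11.2.3 leaves the imputation method to the SAP, and nothing elsewhere overrides the rule. Protocol 10.1.1 describes the composite differently: "Each component score is divided by the baseline SD of that component, to form standardized Z-scores", with no mention of subtracting the mean.

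**The concern.** The rule for summed items has been applied to a score that has no integer grid. A ceiling on a z-score sum can only raise it, so every imputed value of the primary endpoint would be recorded as better than the observed components imply.

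The wording can also be read as ordinary rounding. The FCSRT sentence favours the literal reading by contrast but does not settle it, so two programmers could score the primary endpoint differently.

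The cap is undefined. The components are bounded at 96, 25, 91 and 30, so a maximum on the z-scale exists, but the SAP does not compute it.

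Extending the rule to the CDR-SB is a further error. Its box ratings include 0.5 and a higher score means more impairment, so rounding up makes an imputed CDR-SB look worse while it makes an imputed PACC look better.

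Prorating by 4/3 makes sense only for components with a common centre, so the imputation rule must refer to the centred z-scores of SAP 5.1 and not to the protocol's description.

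**Working it through.** **1. Yardstick.** SAP 6.2 claims, for N = 1150 (1:1), SD 2.85 and 30% attrition, "80% power (5% 2-sided alpha) to detect a treatment difference of 0.532 points". Using completers only, 1150 × 0.7 / 2 = 402.5 per arm and 2.802 × 2.85 × √(2/402.5) = 0.563, which does not match. A repeated-measures variance does match. With ten post-baseline PACC visits, compound symmetry with correlation 0.5 and linear retention to 70%, the variance factor is 1.2685 and the detectable difference is 2.802 × 2.85 × √(2 × 1.2685/575) = 0.530. With SD 3.08 it is 0.573, against 0.570 stated. The covariance and retention pattern are assumptions; SAP 6.2 gives the 0.5 only in its open-label paragraph. The implied standard error is 0.532/(1.960 + 0.842) = 0.190.

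**2. Shift per imputed PACC.** The prorated value is x = (4/3) × (sum of three z-scores). The literal shift is ceil(x) − x.

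- Normal components, 2,000,000 draws per setting, inter-component correlation 0, 0.3 or 0.5, mean decline 0 to 0.6 SD: mean shift +0.500, SD 0.289, range 0 to just under 1.
- Integer-scored components with assumed means and SDs, each component missing in turn: mean +0.494 to +0.502, maximum 0.999.
- Ordinary rounding: mean 0.00, SD 0.289, range −0.5 to +0.5.

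The mean literal shift is 0.5/2.85 = 0.175 SD of the 240-week change.

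**3. Treatment contrast.** The rule is the same in both arms, and for baseline scores SAP 7.9.1.1 states: "The model is constrained to not allow a difference between treatment group means at baseline". The bias is therefore approximately 0.5 × (difference between arms in the share of PACCs imputed near week 240). With d = bias/0.190, two-sided type I error is P(Z > 1.96 − d) + P(Z < −1.96 − d). The documents give no imputation rate, so the differences below are assumed.

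| Assumed difference (percentage points) | Bias (points) | d | Type I error |
|---|---|---|---|
| 0 | 0 | 0 | 0.0500 |
| 1 | 0.005 | 0.03 | 0.0501 |
| 3 | 0.015 | 0.08 | 0.0507 |
| 10 | 0.050 | 0.26 | 0.0580 |

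Type I error reaches 0.055 at a difference of 7.9 percentage points.

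**4. Added variance.** If a share p is imputed, the literal rule adds p/3 − (p/2)². Relative to 2.85² = 8.12, this is 0.04%, 0.20% and 0.38% for assumed p of 1%, 5% and 10%.

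**5. CDR-SB.** The scale "assesses 6 domains: memory, orientation, judgment and problem solving, community affairs, home and hobbies, and personal care". One missing box is 1/6 = 17%, within the SAP's 30% limit; two are 2/6 = 33%, outside it. So only one missing box can be imputed, by a factor of 6/5.

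| Sum of five boxes | Prorated | Rounded up | Added by rounding |
|---|---|---|---|
| 0 | 0 | 0 | 0 |
| 0.5 | 0.6 | 1 | +0.4 |
| 1.0 | 1.2 | 2 | +0.8 |
| 1.5 | 1.8 | 2 | +0.2 |
| 2.0 | 2.4 | 3 | +0.6 |
| 2.5 | 3.0 | 3 | 0 |

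**The case against.** The best reply is that the rule will seldom act and that its effect nearly cancels.

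- **Rarity.** SAP 7.2 asks for every effort to recover missing scores and gives the FCSRT and MMSE their own imputation rules. Protocol 10.1 lets a missed measure be collected within 8 weeks. These provisions do make single-component gaps rarer, and a 10-point imbalance would need at least 10% of one arm's PACCs to be imputed. On the other side, any missing free-recall score leaves the FCSRT missing and so triggers the PACC rule.
- **Standard error.** The 0.532 was planned for an MMRM before the pandemic. SAP 6.2 also gives 94% power at 0.75 points under the spline model, which implies 0.75/(1.960 + 1.555) = 0.213. On that basis d is 0.02, 0.07 and 0.23, type I error is 0.0501, 0.0506 and 0.0563, and 0.055 is reached at 8.9 percentage points. This stands, and it makes a small effect slightly smaller.
- **Conditions.** The type I error figures treat the imbalance as systematic. If treatment affects neither cognition nor component completion, the expected imbalance is zero. The spline contrast also uses all visits, so the bias formula is approximate. Both points stand.
- **Cap.** It was reached in at most 0.001% of imputed values under the assumed baseline figures, so leaving it undefined hardly matters in practice.
- **CDR-SB.** CDR effects are exploratory in Protocol 6.3, and SAP 7.4 places every other analysis below the PACC. No bias in the CDR-SB contrast has been computed.

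These arguments limit the consequences. None makes whole-number rounding suitable for a z-score sum, or resolves the two readings.

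**Conclusion.** The concern holds: the rule contradicts the SAP's own definition of the PACC. Followed literally, it overstates each imputed value by half a point on average; under the other reading it still loses precision for no purpose.

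The consequence for the primary test is small. With equal imputed shares the contrast is unbiased, and for imbalances of a few percentage points the bias is below a tenth of a standard error. Only an imbalance of roughly 8 to 9 percentage points would lift type I error to 0.055. That judgement rests on assumed imputation rates, because the documents give none. The rule should be corrected because it is wrong and ambiguous for the primary endpoint, not because it has been shown to endanger the conclusion.

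**What to change.** In SAP 7.2:

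- **PACC.** Delete the rounding sentence. Define the imputed score as 4/3 times the sum of the three observed z-scores, unrounded, and name the centred z-scores of SAP 5.1. Align the description in Protocol 10.1.1 with that definition.
- **Cap.** Delete it, or define it as the sum over the four components of (component maximum − baseline mean)/baseline SD.
- **CDR-SB and the other prorated scales.** Leave the prorated value unrounded, or round to the nearest valid step (0.5 for the CDR-SB), not always up.

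The cost is a few sentences and one line of code, documented before unblinding. No new data are needed and the sample size is unaffected. Protocol 11.2.1 requires an amendment only when a principal feature changes; other changes to the protocol's statistical methods are justified in the study report.

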7.3. Multicenter Studies

This study will be conducted at multiple centers (investigative sites). No adjustments will be made for multiple sites in the analyses.

7.4. Multiple Comparisons/Multiplicity

The primary analysis is the NCS analysis of the PACC (Section 7.9.1). All other analyses are secondary to this analysis.

7.5. Analysis Populations

The primary and secondary efficacy measures will be analyzed using the mITT population unless otherwise specified. In addition, the PACC will be analyzed using the per-protocol population to verify the robustness of the results. Summaries and analyses for safety measures will be based on the safety population.

[Table A4.SAP.1](#) defines each of the analysis populations used in this study. [Table A4.SAP.2](#) lists the study measures that will be summarized and/or analyzed for each population.

Tabulations of the number and percentage of participants included in each analysis set, by treatment group and overall, will be provided.

Table A4.SAP.1. Analysis Populations for Study A4

Population Name	Description of Population
All Participants Entered	All participants who signed informed consent.
Intent-to-Treat Population (ITT)	All randomized participants.
Modified Intent-to-Treat Population (mITT)	All randomized participants who have a baseline observation and at least one post-baseline observation
Placebo-Controlled Completers Population	All ITT participants who have completed the placebo-controlled study period based on disposition data.
Safety Population	All ITT participants with at least 1 complete or partial infusion of study medication
Per-Protocol Population	All participants in the ITT population who also: 
 • signed the informed consent form • had an assessment of the PACC at each scheduled visit they completed • had no violations of inclusion/exclusion criteria • had no study dosing algorithm violation (such as if participants randomized to treatment A were given treatment B or participants randomized to treatment A never received the assigned study drug) • had less than 20% of infusions incomplete (incomplete infusion = less than 75% of volume infused) • did not miss any more than 10 infusions during the placebo-controlled period • did not miss 3 or more consecutive infusions for reasons other than medical • for placebo-controlled period completers, the treatment duration for the study (that is, Visit 6 through Visit 66) was not more than 240 weeks + 10 days

Abbreviation: PACC = Preclinical Alzheimer Cognitive Composite.

Table A4.SAP.2. Efficacy and Safety Measures Summarized and/or Analyzed for Each Analysis Population

Population Name	Type(s) of Reports
All Participants Entered	Listings of Participant ID, Site/Investigator ID, Informed Consent date
Intent-to-Treat Population (ITT)	Tables, Listings, Figures of the following: participant disposition, participant characteristics at baseline, pre-existing conditions, significant historical diagnoses, concomitant medications.
Modified Intent-to-Treat Population (mITT)	Tables, Listings, Figures of the following: PACC, ADL-Prevention Questionnaire, CFI, CDR-SB, CDR Global Score, C3, MMSE, RUI-B, florbetapir parameters, plasma parameters, vMRI parameters, CSF parameters.
Completers Population	Tables, Listings, Figures of the following: PACC, ADL-Prevention Questionnaire, CFI, CDR-SB, C3, MMSE, RUI-B, florbetapir Parameters, plasma parameters, vMRI parameters, CSF parameters.
Safety Population	Tables, Listings, Figures of the following: exposure and infusion, adverse events, laboratory results, vital signs, weight, ECG, MRI, Immunogenicity, Psychological Well-Being, C-SSRS
Per-Protocol Population	Tables, Listings, Figures of the following: participant characteristics at baseline, PACC.

Abbreviations: ADL = activities of daily living; C3 = computerized cognitive composite; C-SSRS = Columbia-Suicide Severity Rating Scale; CDR-SB = Clinical Dementia Rating - Sum of Boxes; CFI = Cognitive Function Index; CSF = cerebrospinal fluid; ECG = electrocardiogram; ID = identification; MMSE = Mini-Mental State Examination; MRI = magnetic resonance imaging; PACC = Preclinical Alzheimer Cognitive Composite ;RUI-B = Resource Use Inventory, Brief; vMRI = volumetric magnetic resonance imaging.

